3.2.2.1. Adverse events

Adverse Events and SAEs will be collected from time of signature of informed consent form until 30 days after the last dose of study treatment or the start of new anticancer therapy (whichever comes first).

The Medical Dictionary for Regulatory Activities (MedDRA) (MedDRA version 24.0 or later) will be used to code the AEs. AEs will be graded according to the National Cancer Institute Common Terminology Criteria for AEs (NCI CTCAE, latest available version).

Treatment-emergent AEs are defined as those events that occur or worsen on or after the first dose of study drug, through the treatment phase, and until 30 days after the last dose of study treatment or the start of new anticancer therapy (whichever occurs first). AEs occurring before the first administration of IP but increase in severity or frequency on or after administration of IP will be considered as treatment-emergent as well. In the case where it is not possible to define an AE as treatment emergent or not, the AE will be classified by the worst case; i.e. treatment-emergent.

AEs of special interest (AESIs)

The following events are adverse events of special interest (AESIs) for all subjects in this study and must be reported to the sponsor expeditiously irrespective of regulatory seriousness criteria or causality:

Ventricular arrhythmias (e.g., ventricular extrasystoles, ventricular tachycardia, ventricular arrhythmia, ventricular fibrillation, etc.) as defined in Appendix 8.1.1..

Events of Clinical Interest

Some clinical concepts (including some selected individual preferred terms and higher-level terms) have been considered “Events of Clinical Interest” (ECIs) to the acalabrutinib program. ECIs include cardiac events, cytopenias (anemia, leukopenia and thrombocytopenia), hemorrhage, hepatotoxicity, hypertension, infections, intestinal lung disease/pneumonitis, tumor lysis syndrome, and secondary primary malignancies.

These ECIs have been identified as a list of categories provided by the patient safety team. ECIs are defined in Appendix 8.1 and search strategy for narratives are defined in Appendix 8.2.

Other categories may be added as necessary or existing terms may be merged. An AstraZeneca medically qualified expert after consultation with the Global Patient Safety Physician has reviewed the AEs of clinical interest and identified which higher-level terms and which preferred terms contribute to each ECI. Further reviews may take place prior to database lock (DBL) to ensure any further terms not already included are captured within the categories.

3.2.2.2. Exposure and dose interruptions/delay

Total exposure (i.e. duration of treatment or intended exposure), actual exposure, dose withholding and dose reduction will be defined as follows:

- Total (or intended) exposure = min(last dose date where dose > 0 [units], date of death, date of DCO) – first dose date +1
- Actual exposure = intended exposure – number of days where the patient has not taken any study treatment
- Dose withholding is defined as missing doses for ≥ 7 consecutive days.
- Dose reduction is defined as taking a lower dose (100 mg daily) for ≥ 3 consecutive days.

The calculation of actual exposure considers only full days where the patient did not take any study treatment as defined above. It makes no adjustment for reduced dosing frequency, taking lower doses, or any other dose modifications that may have occurred.

Patients who permanently discontinue during a dose interruption

If a patient permanently discontinues study treatment during a dose interruption, then the date of last administration of study medication recorded on DOSDISC will be used in the programming. *See further Appendix 8.2.*

3.2.2.3. Dose intensity

See Appendix 8.3 for example RDI calculations.

Relative dose intensity (RDI) is the percentage of the actual dose delivered relative to the intended dose through to treatment discontinuation. Relative dose intensity (RDI) will be defined as follows:

- RDI = 100% * d/D, where d is the actual cumulative dose delivered up to the actual last day of dosing and D is the intended cumulative dose up to the or the actual last day of dosing. D is the total dose that would be delivered, if there were no modification to dose or schedule.
- The average daily dose is defined as the ratio of actual cumulative dose (d) and the actual duration of exposure.

3.2.2.4. Laboratory data

Clinical safety laboratory assessment is included in Table 4 and specified into the CSP SoA for the timing and frequency.

The clinical chemistry, hematology (see paragraphs below for specific requirements for CLL subjects in Phase 2 – cohort B), pregnancy test, coagulation, urinalysis, hepatitis, HIV and serum immunoglobulin levels analyses will be performed locally at the visits as indicated in the CSP SoA (see Table 1, Table 2 and Table 3), therefore sample volumes may vary according to local practice. If screening assessment clinical chemistry, hematology, coagulation and urinalysis are performed within 5 days prior to the baseline visit (i.e. first dose day: Phase 1 portion- at Cycle 0 Day 1; Phase 2 portion- at Cycle 1 Day 1), they do not need to be repeated at the baseline visit. T/B/NK cell count (ie, CD3, CD4, CD8, CD19, CD16/56) will be performed at the central laboratory, samples will be collected, labelled, stored, and shipped as detailed in the Laboratory Manual.

Table 4 Laboratory variables

Clinical Chemistry ^a	
Calcium	Urea or blood urea nitrogen
Chloride	Uric acid
Magnesium	Creatinine
Phosphate/Phosphorus	Total bilirubin
Potassium	Glucose
Sodium	Albumin
AST	Total protein
ALT	Triglycerides
Alkaline phosphatase (ALP)	Cholesterol

Gamma glutamyl transferase (GGT)	Lactate dehydrogenase (LDH)
Hematology^b	
White blood cell (WBC) count with differential	Platelet count
Red blood cell (RBC) count	Absolute neutrophil count (ANC)
Hematocrit	Absolute lymphocyte count (ALC)
Hemoglobin	
Urinalysis	
pH	Bilirubin
Specific gravity	Protein
Glucose	Ketones
Blood	
Pregnancy Test (females of childbearing potential only)	
Urine human chorionic gonadotropin (hCG) or Serum β hCG	
Hepatitis B and C Testing^c	
HBsAg	Hepatitis B surface antibody (HBsAb)
Anti-HBc	Hepatitis C (hepatitis C virus [HCV]) antibody
Hepatitis B PCR (clinically indicated)	Hepatitis C PCR (clinically indicated)
Coagulation	
Coagulation tests: prothrombin time (PT)	Activated partial thromboplastin time (aPTT)
Fibrinogen	
Other Tests	
T/B/NK Cell Count	Serum immunoglobulin levels
HIV antibody	β 2-microglobulin ^d
Cytogenetics and FISH Panel ^{d,e}	Genetic and molecular prognostic molecules ^{d,f}

a. In case a subject shows an AST or ALT $\geq 3 \times$ ULN together with total bilirubin $\geq 2 \times$ ULN please refer to CSP Appendix D. 'Actions required in cases of increases in liver biochemistry and evaluation of Hy's Law', for further instructions.

b. Hematology will be evaluated at the central laboratory for CLL subjects in Phase 2 – cohort B.

c. Hepatitis serology testing must include HBsAg, HBsAb, anti-HBc and hepatitis C (HCV) antibody. In addition, any subjects testing positive for anti-HBc must have quantitative PCR testing for HBV DNA during screening and monthly basis from Cycle 2 through 19. After Cycle 19, monitoring will occur every 3 months. HBV monitor should continue until 12 months after last dose of study drug (see CSP Table 1, Table 2, Table 3 and exclusion criterion #7). Any subject with a rising viral load (above lower limit of detection) should discontinue study drug and have antiviral therapy instituted and a consultation with a physician with expertise in managing hepatitis B. Since IVIG may cause false positive hepatitis serology, monthly PCR testing is not required in subjects who are currently receiving or received prophylactic IVIG within 3 months before study enrollment and have a documented negative anti-HBc test before the initiation of IVIG therapy. PCR testing should be performed when clinically indicated (eg, in the setting of rising transaminase levels). Refer to CSP Table 1, Table 2 and Table 3 regarding monitoring of subjects who are anti-HBc positive or who have a known history of HBV.

Subjects with a known history of hepatitis C or who are hepatitis C antibody positive should have quantitative PCR testing for HCV RNA performed during screening. No further testing is necessary if the PCR results are negative at screening.

d. These tests will be performed at the central laboratory and for CLL subjects in cohort B only.

e. Cytogenetics and FISH Panel include 17p del, 13q del, trisomy 12, 11q del by FISH and stimulated karyotyping.

f. Genetic and molecular prognostic molecules panel include, but is not limited to, sequencing of p53 mutations, immunoglobulin heavy-chain variable (IGHV) mutational status.

3.2.2.5. Physical examinations

The physical examination includes height (Screening only) and weight, and examination of the skin, eyes, ears, nose, throat, lungs, heart, abdomen, extremities, musculoskeletal, nervous, lymphatic system, and general appearance. The lymphatic system examination will include examination of palpable lymph nodes and spleen and liver below the costal margin on the respective side. Physical examination will be performed at timelines as specified in the SoA.

3.2.2.6. Vital signs

Vital signs (Blood pressure, pulse rate, and body temperature) will be assessed after at least 5 minutes of rest for the subject in a quiet setting without distractions (eg, television, cell phones).

3.2.2.7. ECG

Twelve-lead ECG will be obtained as outlined in the SoA (see CSP Section 1.1) using an ECG machine that automatically calculates the heart rate and measures PR, QRS, QT, and QTc intervals.

3.2.2.8. ECOG performance status

ECOG performance status will be assessed at screening, prior to the first dose of study treatment and at all visits thereafter according to ECOG criteria as follows:

Grade	ECOG

0	Fully active, able to carry on all pre-disease performance without restriction
1	Restricted in physically strenuous activity but ambulatory and able to carry out work of a light or sedentary nature, eg, light house work, office work
2	Ambulatory and capable of all self-care but unable to carry out any work activities. Up and about more than 50% of waking hours
3	Capable of only limited self-care, confined to bed or chair more than 50% of waking hours
4	Completely disabled. Cannot carry on any self-care. Totally confined to bed or chair
5	Dead

3.2.3. Pharmacokinetic variables

Pharmacokinetic analysis of the plasma concentration data for acalabrutinib and a metabolite (ACP-5862) will be performed by Covance (Contract Research Organization) on behalf of AstraZeneca.

In Phase 1 portion, venous blood samples for determination of concentrations of acalabrutinib and its metabolite (ACP-5862) in plasma will be taken at the times presented in Table 11 and Table 12 of CSP.

Where possible, the following PK parameters will be estimated using non-compartmental method with plasma concentration data of acalabrutinib and a metabolite (ACP-5862) on Cycle 0 Day 1 and Cycle 1 Day 8 of Phase 1:

- Maximum observed plasma drug concentration (C_{max})
- Time to reach maximum observed drug concentration (t_{max})
- Terminal elimination rate constant (λ_Z)
- Half-life associated with terminal slope (λ_Z) of a semilogarithmic concentration-time curve ($t^{1/2}\lambda_Z$)
- Area under the plasma concentration-time curve from zero to 12 hours (AUC₀₋₁₂)
- Area under the plasma concentration-time curve from zero to the time of the last measurable concentration (AUClast)
- Area under the plasma concentration-time curve from zero to infinity (AUC_{inf})
- Apparent total body clearance of drug from plasma after extravascular administration (CL/F)
- Volume of distribution (apparent) following extravascular administration (based on terminal phase) (V_{Z/F})

- Accumulation ratio for AUC calculated as $AUC_{\tau}(\text{steady state})/AUC_{\tau}(\text{first dose})$ and denoted by Rac AUC
- Accumulation ratio calculated as $C_{\max}(\text{steady state})/C_{\max}(\text{first dose})$ and denoted by Rac Cmax
- Temporal change parameter (TCP) calculated as $AUC_{\tau}(\text{steady state})/AUC_{\text{inf}}(\text{first dose})$
- Metabolite: Parent ratio for AUC calculated as $AUC(\text{metabolite})/AUC(\text{parent})$
- Metabolite: Parent ratio for Cmax calculated as $C_{\max}(\text{metabolite})/C_{\max}(\text{parent})$
- Diagnostic parameters:
 - $\lambda z N$: number of data points used for λz determination
 - λz lower: lower (earlier) t used for λz determination
 - λz upper: upper (later) t used for λz determination
 - λz span ratio: time period over which λz was determined as ratio of $t^{1/2}/\lambda z$
 - Rsq: statistical measure of fit for the regression used for λz determination
 - Rsq adj.: statistical measure of fit for the regression used for λz determination adjusted for the number of used data points
 - AUC_{extr} : extrapolated area under the curve from t_{last} to infinity, expressed as percentage of AUC_{inf}
 - t_{last} : time of last observed (quantifiable) concentration

The C_{\max} and t_{\max} will be determined by inspection of the concentration-time profiles. Where possible the λz will be calculated by log-linear regression of the terminal portion of the concentration-time profiles where there are sufficient data, and the $t^{1/2}/\lambda z$ will be calculated as $\ln 2/\lambda z$. The AUC_{0-12} , and AUC_{last} will be calculated using the linear/log trapezoidal rule (i.e. “linear-up-log-down”: the linear trapezoidal rule is used any time that the concentration data is increasing, and the logarithmic trapezoidal rule is used any time that the concentration data is decreasing). Where appropriate, the AUC_{last} will be extrapolated to infinity using λz to obtain AUC_{inf} . The CL/F will be determined from the ratio of dose/AUC. The Vz/F will be determined from the ratio of $CL/F/\lambda z$. The Rac AUC and Rac Cmax will be calculated as the ratio of the AUC_{τ} or C_{\max} on Cycle 1 Day 8 and Cycle 0 Day 1, respectively. The TCP will be assessed by the calculation of the ratio of AUC_{τ} on Cycle 1 Day 8 and AUC_{inf} on Cycle 0 Day 1. The Metabolite: Parent ratio parameters will be calculated after molar conversion.

3.3. Phase 2

3.3.1. Efficacy variables

3.3.1.1. Best overall response (BOR)

Best overall response is the best visit response a patient has had following first dose date, but prior to starting any subsequent anticancer therapy up to and including progression or the last evaluable assessment in the absence of progression, assessed by BICR. To determine the BOR, the following order is used:

- For R/R MCL patients: CR > PR > SD > PD > NE.
- For R/R CLL patients: CR > CRi > nPR > PR > PRL > SD > PD > NE.

Patients will be assigned a BOR of NE (Non-Evaluable) if all post-baseline responses are either missing (not documented) or documented as NA (Not Applicable) or Unknown.

3.3.1.2. Overall response rate (ORR) as assessed by BIRC

For R/R MCL subjects, ORR will be defined as the proportion of subjects who achieve either a CR or PR as BOR in the tumor response analysis set, according to the Lugano Classification for NHL (Cheson 2014), as assessed by BICR.

For R/R CLL subjects, ORR will be defined as the proportion of subjects who achieve a CR, CRi, nPR, PR, as BOR in the tumor response analysis set, according to iwCLL 2018 criteria (Hallek 2018) as assessed by BICR.

Data obtained up until progression, or last evaluable assessment in the absence of progression, will be included in the assessment of ORR. Patients who discontinue treatment without progression, receive a subsequent anti-cancer therapy and then respond will not be included as responders in the ORR.

ORR plus patients with a best overall response of PRL will also be assessed, denoted as ORR+PRL.

3.3.1.3. Duration of Response (DoR) as assessed by BIRC

DoR is defined as the interval from the first documentation of objective response (PR or better) mentioned above to the earlier of the first documentation of objective disease progression by the BICR or death from any cause.

Subjects who withdraw from the study or are considered lost to follow-up without prior documentation of disease progression will be censored on the date of the last adequate disease assessment. Subjects who start new anticancer therapy before documentation of disease progression will be censored on the date of the last adequate disease assessment that is on or before the start date of the new anticancer therapy.

- For BICR assessments, the date of progression will be determined based on the **earliest** of the scan dates of the component that triggered the progression for the adjudicated reviewer selecting PD or of the reviewer who read baseline first if there is no adjudication for BICR data.
- For investigator assessments, the date of progression will be determined based on the **earliest** of the dates of the component that triggered the progression.
- For both BICR and investigator assessments, when censoring a patient for DoR the patient will be censored at the **latest** of the dates contributing to a particular overall visit assessment.

Table 5 Censoring rules for DoR

Assessment	Outcome	Date of progression or censoring
Documented PD between scheduled visits on or before receiving subsequent anticancer therapy or data cutoff, whichever occurred first	Event	Earliest date of disease assessment documenting progression
Death without documented PD and not receiving subsequent anticancer therapy on or before data cutoff	Event	Date of death
Documented PD or death after subsequent anticancer therapy and the subsequent anticancer started before data cutoff date	Censored	Date of last adequate disease assessment prior to subsequent anticancer treatment
No documented PD or death at the time of data cutoff and subsequent anticancer therapy started before the data cutoff	Censored	Date of last adequate disease assessment prior to subsequent anticancer treatment
Documented PD or death after subsequent anticancer therapy and the subsequent anticancer started after data cutoff date	Censored	Date of last adequate disease assessment on or before data cutoff
No documented PD or death at the time of data cutoff and subject not received subsequent anticancer therapy or subsequent anticancer therapy started after the data cutoff	Censored	Date of last adequate disease assessment on or before data cutoff
Withdrew consent without documented PD or death	Censored	Date of last adequate disease assessment
Lost to follow-up without documented PD or death	Censored	Date of last adequate disease assessment
Documented PD or death after 2 or more consecutively missed visits following the first documentation of objective response	Censored	Date of last adequate disease assessment before the consecutively missed visits

PD = progressive disease

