8.1.1.2 CLL tumor assessment

Overall response assessments for CLL subjects will be based upon evaluation of physical exams, recording of symptoms, radiologic evaluations, and hematologic evaluations per the Schedule of Activities. Subjects who have signs and symptoms of disease progression outside of the scheduled study visits and assessments should be evaluated by the Investigator with a physical exam and a CBC with differential to determine if disease progression is present. The blood samples for response or disease progression determination should be confirmed by a central laboratory (not applicable for Phase 1 CLL subjects; samples from local laboratories can be used if central testing is unavailable). Any suspected case of disease progression (in the absence of laboratory or histopathologic changes meeting the criteria for PD) should be confirmed with a CT scan and should be reported to the Sponsor or designee. In addition,

when clinically appropriate, based on Investigator-perceived risk-benefit assessment, a subject may continue treatment and remain under close observation until progression is confirmed. New anticancer therapy should be withheld if clinically appropriate in the absence of confirmed progressive disease.

Baseline:

For baseline, a CT scan with contrast (MRI should be used if contraindicated) is required to cover the neck, chest, abdomen, and pelvis and any other disease sites (e.g. brain), within 28 days before the first dose of study drug. Spleen and liver size should be recorded in CT measurement. Additionally, bone marrow aspiration and biopsy within 3 months before first dose of study drug is required. Physical exam (especially lymph node and organomegaly), B symptoms, blood counts with differential and other clinical information should be recorded in the eCRF at the baseline. PET-CT is not required, but if performed within 60 days before the study treatment, should be recorded in eCRF.

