	Constitutional symptoms	None	Any	Any	Any
	Circulating lymphocyte count	Normal	Decrease \geq 50% from baseline	Increase \geq 50% over baseline	Change of -49% to +49%
B	Platelet count	\geq 100,000/ μ L	\geq 100,000/ μ L or increase \geq 50% over baseline	Decrease of \geq 50% from baseline secondary to CL	Change of -49% to +49%

	Hemoglobin	≥ 11.0 g/dL (untransfused and without erythropoietin)	≥ 11 g/dL or increase $\geq 50\%$ over baseline	Decrease of ≥ 2 g/dL from baseline secondary to CLL	Increase <11.0 g/dL or $<50\%$ over baseline, or decrease >2 g/dL
	Marrow	Normocellular, no CLL cells, no B-lymphoid nodules	Presence of CLL cells, or of B-lymphoid nodules, or not done	Increase of CLL cells by $\geq 50\%$ on successive biopsies	No change in marrow infiltrate

Abbreviations: CLL=chronic lymphocytic leukemia; CR=complete response; CT=computed tomography; PD=progressive disease; PR=partial response; SD=stable disease.

Note: CR, complete remission: all of the criteria have to be met; PR, partial response: for a PR at least 2 of the parameters of group A and 1 parameter of group B need to improve if previously abnormal. If only one parameter of both groups A and B is abnormal prior to therapy, only 1 needs to improve. PD, progressive disease: at least one of the above criteria of group A or group B has to be met; SD, stable disease: all of the above criteria have to be met. Constitutional symptoms alone do not define PD.

- a. Sum of the products of 6 or less lymph nodes (as evaluated by CT scans and physical examination in clinical trials, or by physical examination in general practice).
- b. Spleen size is considered normal if <13 cm. There is not firmly established, international consensus of the size of a normal liver; therefore, liver size should be evaluated by imaging and manual palpation in clinical trials and be recorded according to the definition used in a study protocol.

* CRi (CR with incomplete bone marrow recovery) refers to subjects who fulfill all the criteria for a CR (including the bone marrow examinations), but have a persistent anemia, thrombocytopenia, or neutropenia apparently unrelated to CLL, but related to drug toxicity. Subjects who are otherwise in a complete remission, but bone marrow nodules can be identified histologically, should be considered to have “nodular PR” (nPR).

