4.2.2.4. Duration of response (DoR)

The analysis of BICR-assessed DoR will be estimated using the Kaplan-Meier (KM) methods will be performed on R/R MCL patients (phase 1 and phase 2 combined) and phase 2 R/R CLL patients separately. KM estimates will be calculated for event time quartiles (including median, Q1 and Q3), and event-free rates will be calculated at selected time points (i.e. 6 months, 12 months, 18 months).

In addition, type of event (i.e. death, PD) and the reason for censoring (i.e. data cutoff, lost to follow-up, subsequent anticancer therapy) will be summarized in the same table. Please refer Table 5 for censoring rules.

Kaplan-Meier plot for duration of response will be created accordingly. In addition, Kaplan-Meier plot for duration of response by best overall response (PR and CR) will be developed in a separated plot.

The analysis will be performed on the tumor response set.

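### SAP 3.3.1.3 dates BICR progression by scan dates only, which leaves Cohort B progression met by blood counts or marrow with a late date, no date, or no BICR event

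*SAP*

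**What the plan says.** SAP 3.3.1.3 gives two progression-date rules. For BICR, the date is the earliest "of the scan dates of the component that triggered the progression for the adjudicated reviewer selecting PD"; without adjudication, the reader who read baseline first supplies it. For the investigator, it is the earliest date of the triggering component, with no restriction to scans. The BICR rule is not limited to MCL. Table 5 in the same section dates a documented progression at the "Earliest date of disease assessment documenting progression", again without a scan restriction.

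For CLL, the note to SAP Table 3 reads: "PD, progressive disease: at least one of the above criteria of group A or group B has to be met". Group B is platelets, haemoglobin and marrow. Protocol 8.1.1.2 states: "The blood samples for response or disease progression determination should be confirmed by a central laboratory". It asks for CT confirmation of suspected progression only "in the absence of laboratory or histopathologic changes meeting the criteria for PD) should be confirmed with a CT scan". SAP 3.1.3 asks for CT confirmation of any suspected progression and omits that exception.

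On what BICR reads, the documents point two ways. SAP 3.1.3 and Protocol 8.1.1.2 describe a central imaging service giving radiologic assessments, and SAP 3.1.3 leaves details to the BICR Charter. SAP 3.3.1.1 nevertheless has BICR assign "For R/R CLL patients: CR > CRi > nPR > PR > PRL > SD > PD > NE".

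SAP 4.2.2.4 plans Kaplan-Meier DoR, and "event-free rates will be calculated at selected time points (i.e. 6 months, 12 months, 18 months").

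**The concern.** The scan-date rule suits a lymphoma whose progression is read from images. In CLL, a fall in platelets or haemoglobin secondary to the disease, or a marrow finding, can meet progression with no scan involved. No passage says how BICR should date it.

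If the bullet is followed literally, the event moves to a later scan. It may also be lost: a subject withdrawn for progression passes to survival contact under Protocol 7.1.2, with no further scheduled CT, and Table 5 censors a subject who starts new therapy before a BICR progression is documented. Either route lengthens BICR DoR. It could also make the BICR and investigator analyses differ because of a dating convention rather than a difference in judgement.

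**Working it through.** **1. The plan's own figure.** Cohort B has n = 60, a null ORR of 70% and an alternative of 88%. The smallest count r with P(X ≥ r | 0.70) ≤ 0.025 is 50 (exact alpha 0.0139). Power is P(X ≥ 50 | 0.88) = 0.9006, which reproduces the stated 90%. Progression dates do not enter this calculation.

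**2. The rules side by side, for a progression triggered in Cohort B by counts or marrow.**

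| Rule | Date it gives |
|---|---|
| SAP 3.3.1.3, BICR bullet | a scan date, so a later one or none |
| SAP 3.3.1.3, investigator bullet | date of the count or marrow |
| SAP Table 5 | date of the assessment that documented it |

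- *BICR uses non-imaging data.* CRi needs counts and marrow, nPR needs marrow, and PRL needs a lymphocyte count plus platelets or haemoglobin. The first row then disagrees with the other two.
- *BICR reads images only.* Every BICR trigger is a scan, so the BICR bullet and Table 5 agree. Progression by counts or marrow is then never a BICR event, although SAP Table 1 describes BICR DoR and PFS as assessed per iwCLL 2018.

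**3. Length of the delay.** Under Protocol 8.1.1.2 responders have CT 12 weeks after first response, then every 24 weeks (±7 days). Protocol Table 3 schedules visits with haematology every 12 weeks (±2 days). Counted from first response:

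- CT: weeks 12, 36, 60, 84
- visits without CT: weeks 24, 48, 72

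The nominal gap is 12 weeks, or 84 days. With windows it is 84 ± (2 + 7) = 75 to 93 days, about 11 to 13 weeks. An unscheduled visit soon after a scan can precede the next CT by up to about 24 weeks (plus 7 days).

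**4. Position against the planned DoR time points** (month = 30.4375 days).

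| Visit without CT | Time point | Next CT | Margin before / after |
|---|---|---|---|
| 168 d (5.5 mo) | 6 mo = 182.6 d | 252 d (8.3 mo) | 14.6 / 69.4 d |
| 336 d (11.0 mo) | 12 mo = 365.25 d | 420 d (13.8 mo) | 29.2 / 54.8 d |
| 504 d (16.6 mo) | 18 mo = 547.9 d | 588 d (19.3 mo) | 43.9 / 40.1 d |

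Allowing 7 days for the response CT and 2 for the visit, the margins before fall to 5.6, 20.2 and 34.9 days. Allowing 7 days at each CT, the margins after fall to 55.4, 40.8 and 26.1 days. A progression dated at the visit therefore falls before the time point, and the next CT after it. If it is dated instead at a marrow taken more than about 1 to 2 weeks after the visit, the 6-month crossing is lost.

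**5. Effect of one such event.** The responder count N is an assumption: 42 (70% of 60), 53 (88%) or 58 (about 97%).

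- *Moved past the time point, no earlier censoring:* 100/N = 2.4, 1.9 and 1.7 points.
- *Censored at the previous CT:* the Kaplan-Meier estimate rises by S(t) / (N·S(c) − 1), where c is the time of that CT and no one else is censored. Assuming a constant hazard, N = 53, t = 6 months, c = 84 days and S(t) = 0.70: S(c) = 0.70^(84/182.6) = 0.849, and the rise is 0.70 / (53 × 0.849 − 1) = 1.6 points. With true rates of 70% to 90% and all three time points, the range is 1.6 to 1.9 points.

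**The case against.** The strongest reply is that the rules do not conflict. Table 5 also serves the investigator analysis, so its wording has to be general; the bullets then specialise it for each assessor, and a scan is a disease assessment. If BICR reads images only, both give the same date. This stands as far as it goes: a reader might infer that the SAP plainly contradicts itself, and the documents do not support that without the Charter. They support a conditional conflict or, failing that, an unstated restriction of the endpoint.

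Second, for responders the overall response assessment follows the CT schedule, and only clinical assessments remain at the visits without CT. No BICR time point is scheduled there, and rewording the date rule would not create one. This also stands. It limits how often the delay would arise, though Protocol 8.1.1.2 does provide for progression evaluation outside scheduled assessments.

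Third, investigator DoR already uses the triggering component and is analysed by the same methods, so a comparison is built in. That softens the consequence but does not correct the BICR estimate.

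Fourth, following the SAP 3.1.3 sentence would put a CT at suspicion and remove most of the delay. That is true, but Protocol 8.1.1.2 differs on this, so it cannot be relied on.

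**Conclusion.** The concern holds in a limited form. The bullet fits MCL but does not handle Cohort B progression met by counts or marrow, whichever way BICR works: it gives a late or missing date if BICR uses non-imaging data, and no BICR event if it does not.

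The size is modest. Each affected subject would move an event-free rate by about 2 points, given 42 to 58 responders and a progression first documented at a scheduled visit without CT. How many there would be is not given. It is probably few, because Protocol 8.1.1.2 says lymphocytosis alone is not progression and Table 3 requires cytopenia to be secondary to CLL. Death remains an event under the Table 5 row "Death without documented PD and not receiving subsequent anticancer therapy on or before data cutoff".

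Two stronger inferences are not supported. One is that BICR DoR is inflated by a known amount: the number of such events is unknown and a CT at suspicion may remove the delay. The other is that PFS is misdated in the same way: SAP 3.3.1.4 and Table 6 do not repeat the scan-date bullet, so PFS is affected only if it is carried across.

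DoR is secondary and descriptive, and ORR, sample size and power are untouched. The priority lies between an optional clarification and a recommended change. Confidence is medium, because the BICR Charter was not available.

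**What to change.** First check the BICR Charter for whether central review receives haematology, examination and marrow data.

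- **If it does:** in SAP 3.3.1.3, for Cohort B, date BICR progression at the earliest date of the component that triggered it (scan, central haematology, physical examination, marrow or biopsy), in line with Table 5. Keep the scan-date rule for MCL. State in 3.3.1.4 that Table 6 is applied the same way.
- **If it is imaging only:** add no new central adjudication. State in the SAP that BICR DoR and PFS in Cohort B capture radiologic progression only, and refer to the investigator-assessed DoR and PFS for non-radiologic progression.

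In either case, reconcile the CT-confirmation sentence in SAP 3.1.3 with Protocol 8.1.1.2.

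The cost is SAP wording and the Charter check, plus, in the first case, some derivation programming on data already collected. In that case BICR DoR may become slightly shorter.
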